8.1 Efficacy / response assessments and criteria

Baseline assessments must occur within \leq 7 days of protocol therapy initiation as indicated in Section 8, schedule of assessments. Response assessments include serum protein electrophoresis (SPEP), serum free light chains (sFLCs), 24 h urine protein electrophoresis with m-spike (24h UPEP), serum and urine immunofixation, and, for confirmation of complete remission and to monitor asecretory myeloma; bone marrow examinations.

Efficacy assessments are scheduled to occur after each cycle except for bone marrow examinations which are done only for confirmation of complete remission (once) and in patients

with measurable disease restricted to bone marrow plasma cell percentage, where bone marrow is obtained after cycle 2 and at study completion.

All response categories require two consecutive blood and urine assessments (bone marrow biopsies do not need to be repeated) and no evidence for progressive or new bone lesions if radiographic studies were performed. Radiographic studies are not required for response assessment but should be obtained when there is clinical suspicion for progressive bone disease. The time point myeloma response parameters first fall into respective response levels is recorded as the time a response is achieved once a consecutive set of tests confirmed the response. For response categories \geq PR the confirmatory test may be obtained at any time but will generally be obtained at the start of the next cycle unless there is a clinical reason to obtain earlier; for MR consecutive tests have to confirm MR over a period of at least 6 weeks.

Complete response (CR)	Negative immunofixation of serum and urine (or normal sFLC ratio if the only measurable disease outside of the bone marrow is by sFLCs) and disappearance of any soft tissue plasmacytomas, and $<5\%$ plasma cells in bone marrow
Stringent CR (sCR)	CR as defined above plus normal sFLC ratio and absence of clonal cells in bone marrow by immunohistochemistry or immunofluorescence
Very good partial response (VGPR)	Serum and urine M-component detectable by immunofixation but not on electrophoresis or $\geq 90\%$ or greater reduction in serum M-component plus urine M-component $<100\text{mg}$ per 24 h or $>90\%$ reduction in the difference between involved and uninvolved serum free light chains if this is the only measurable disease outside of the bone marrow
Partial response (PR)	$\geq 50\%$ reduction of serum M protein and reduction in 24-h urinary M protein by $\geq 90\%$ or to $<200\text{mg}$ per 24 h, if the serum and urine M protein are unmeasurable, a $\geq 50\%$ decrease in the difference between involved and uninvolved sFLC levels is required in place of the M protein criteria, if the only measurable disease is in the bone marrow, a $\geq 50\%$ reduction in bone marrow plasma cells is required, provided the baseline percentage was $\geq 30\%$. In addition to the above criteria, if present at baseline, a $\geq 50\%$ reduction in the size of soft tissue plasmacytomas is required.
Minor response (MR)	$\geq 25\%$ but $\leq 49\%$ reduction of serum M protein and reduction in 24 h urine M protein by 50–89%, which still exceeds 200mg per 24 h. In addition to the above criteria,

if present at baseline, 25–49% reduction in the size of soft tissue plasmacytomas is also required. No increase in size or number of lytic bone lesions (development of compression fracture does not exclude response).

Stable disease (SD)

Not meeting criteria for sCR, CR, VGPR, PR, MR, or progressive disease (see under 5.9.1).

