6.1.2 Inclusion and exclusion criteria

Patients must have baseline evaluations performed prior to the first dose of study drug and must meet all inclusion and exclusion criteria. Results of all baseline evaluations, which assure that all inclusion and exclusion criteria have been satisfied, must be reviewed by the Principal Investigator prior to enrollment of that patient. In addition, the patient must be thoroughly informed about all aspects of the study, including the study visit schedule and required evaluations and all regulatory requirements for informed consent. The written informed consent must be obtained from the patient prior to enrollment. The following criteria apply to all patients enrolled onto the study unless otherwise specified.

Inclusion criteria

1. Male or female patients aged ≥ 18 years old
2. Ability to provide written informed consent obtained prior to participation in the study and any related procedures being performed
3. Patients must carry a diagnosis of symptomatic multiple myeloma according to international myeloma working group criteria⁵⁰ and have relapsed or refractory disease according to international uniform response criteria and must have previously received therapy with a proteasome inhibitor and an IMiD™^{51,52}(see also 6.2).
4. Must have measurable disease defined as any of the following: Serum m-spike ≥ 1 g/dL, 24 h urine m-spike of at least 200mg/d, involved serum free light chains ≥ 100 mg/L with abnormal serum free light chain ratio, bone marrow plasma cells of at least 30%
5. ECOG PS ≤ 2
6. No gastro-intestinal condition, that in the opinion of the treating physician or the principal investigator significantly limits oral absorption
7. No serious uncontrolled coexisting medical condition

8. Patients must meet the following laboratory criteria:
 - $ANC \geq 1.0 \times 10^9/L$ without use of pegfilgrastim in the preceding 21 days and without non-pegylated G-CSF or GM-CSF within 7 days prior to study entry
 - Hemoglobin ≥ 8 g/dl (may be after transfusion of packed red blood cells or use of erythropoiesis stimulating agents)
 - Platelets $\geq 70 \times 10^9/L$ without platelet transfusion 7 days prior to study entry
 - AST and ALT $\leq 2.5 \times$ ULN
 - Serum bilirubin $\leq 1.5 \times$ ULN

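### The first VGPR alternative in Section 8.1 requires no change from baseline, so an unchanged patient measurable only by free light chains or marrow could be scored above PR

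*Combined protocol and SAP*

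**What the plan says.** Section 8.1 gives VGPR three alternatives, joined by *or*:

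1. "Serum and urine M-component detectable by immunofixation but not on electrophoresis";
2. a serum M-component reduction of at least 90% with a urine M-component below 100 mg per 24 h;
3. a more than 90% "reduction in the difference between involved and uninvolved serum free light chains if this is the only measurable disease outside of the bone marrow".

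Under inclusion criterion 4 (Section 6.1.2), any one of four measures is enough for entry. Two are M-spike thresholds (serum at least 1 g/dL, urine at least 200 mg/d). The other two are "involved serum free light chains ≥ 100 mg/L with abnormal serum free light chain ratio, bone marrow plasma cells of at least 30" per cent. A patient can therefore enter without an M-spike.

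The PR row in Section 8.1 handles these patients explicitly. If serum and urine M-protein are unmeasurable, a fall of at least 50% in the difference between involved and uninvolved sFLC (dFLC) "is required in place of the M protein criteria". Also, "if the only measurable disease is in the bone marrow", marrow plasma cells must fall by at least 50%. SD is residual: "Not meeting criteria for sCR, CR, VGPR, PR, MR, or progressive disease".

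Section 13.1.2.1 counts VGPR in both the response rate (RR) and the clinical benefit response rate. Section 4.2 compares each cycle's panel with screening. Section 8.1 requires two consecutive sets of blood and urine tests for every category.

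**The concern.** The first VGPR alternative can be satisfied by where a patient stands, without any movement. Some patients admitted under criterion 4 may stand there already. The dFLC alternative does not prevent this: because it is joined by *or*, it adds a route to VGPR for sFLC-only patients without closing the first one. For marrow-only patients VGPR has no rule of its own.

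The result is an inverted hierarchy, in which a patient with no improvement fails PR but meets the category above it. VGPR counts as a response, so any such coding raises the RR. Section 2 gives a firmer estimate of activity as one reason for the 20-patient phase II extension. Two assessors applying Section 8.1 in good faith could also code the same patient differently, one as VGPR and one as SD.

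**Working it through.** The plan gives no sample-size or precision calculation for response, so there is no stated figure to reproduce. The check applies the Section 8.1 rows to two hypothetical eligible patients with entirely unchanged disease. Both have serum and urine immunofixation positive and nothing visible on electrophoresis.

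| Category | sFLC-only, unchanged | Marrow-only, unchanged |
|---|---|---|
| CR/sCR | No: sFLC ratio still abnormal | No: immunofixation positive, marrow not below 5% |
| VGPR, first alternative | **Met** | **Met** |
| VGPR, second alternative | No: no M-component reduction | No: no M-component reduction |
| VGPR, third alternative | No: 0% dFLC fall against >90% | Does not apply |
| PR | No: 0% dFLC fall against ≥50% | No: 0% marrow fall against ≥50% |
| MR | No: no M-protein reduction | No: no M-protein reduction |
| PD | No: no increase | No: no increase |
| SD | Unavailable, because VGPR is met | Unavailable, because VGPR is met |

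Confirmation does not remove the problem. Table 8-1 places response panels at screening and on day 1 of cycle 2 and later cycles. An unchanged patient meets the first alternative at cycle 2 day 1 and again at cycle 3 day 1, which satisfies the two-panel rule.

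**Size per patient.** A patient who would otherwise be a non-responder adds 1/N to the RR:
- phase II: 1/20 = 5.0 percentage points;
- whole study: 1/31 = 3.2 percentage points.

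**Illustration.** Take 5 true responders in 20. This is an assumption, near the 24% historical rate quoted in Section 2 (0.24 × 20 = 4.8). The number misclassified, k, is not in the documents; 0 to 4 is an assumed range. Intervals are exact (Clopper-Pearson) 95%.

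| k | Reported RR | 95% CI |
|---|---|---|
| 0 | 5/20 = 25% | 8.7 to 49.1 |
| 1 | 6/20 = 30% | 11.9 to 54.3 |
| 2 | 7/20 = 35% | 15.4 to 59.2 |
| 4 | 9/20 = 45% | 23.1 to 68.5 |

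**Phase I.** Section 2 reports one PR, two MR and one six-month SD among 11 patients. The RR is 1/11 = 9.1% (95% CI 0.2 to 41.3), with no VGPR listed.

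**The case against.** The strongest reply is that Section 8.1 should be read with the rest of the protocol. Section 4.2 makes response a comparison with screening. Section 8.1 schedules efficacy assessment after each cycle, dates a response from when the parameters first enter a category, and speaks of categories at or above PR, which implies an ordering. On that reading an unchanged panel is not a response. This is good evidence of intent, but none of these provisions sets a minimum change for VGPR or says that VGPR also requires PR. Section 8.1 remains the place where the categories are defined. The protocol also cites international response criteria; whether those supply the missing baseline condition cannot be checked from these documents.

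Several objections do stand, and they limit the point:

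- A reader might infer that such patients are already VGPR at screening or on day 1. They are not: screening is the comparator, and a response needs two post-baseline panels.
- A reader might infer that any positive immunofixation is enough. As worded, the first alternative needs the M-component in both serum and urine, so a patient positive in only one does not meet it.
- Below the measurability threshold is not the same as invisible. A serum spike under 1 g/dL that still shows on electrophoresis fails the first alternative.
- Marrow-only patients with truly non-secretory disease have no M-component on immunofixation and cannot meet it either.

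**Conclusion.** The drafting gap is real, but the group it affects is narrow. As written, Section 8.1 allows an unchanged sFLC-only or marrow-only patient to be coded VGPR when serum and urine immunofixation are both positive and electrophoresis shows nothing. It also rules out SD for that patient. This conflicts with the PR row and with the comparison to screening in Section 4.2. Any resulting bias in the RR is upward: 5.0 percentage points per affected patient in phase II, or 3.2 overall, provided the patient would otherwise be a non-responder.

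The number affected is unknown and, given the limits above, probably small. A reader might infer that the phase II rate will be materially inflated, or even doubled. That would rest on assumed frequencies for which the documents have no source. Nor do the documents show that phase I results are affected, since no VGPR was reported. They do not say how many of the 11 patients had sFLC-only or marrow-only disease, so phase I does not show the rule to be safe either. No fault is shown in the second VGPR alternative, which already demands a 90% reduction.

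Severity is minor to moderate. Response is a secondary endpoint reported descriptively with no decision rule, so no error rate, sample size or trial decision changes.

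**What to change.** Amend the VGPR row of Section 8.1 in three respects:

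- Limit the first alternative to patients whose M-protein was detectable on electrophoresis at screening.
- For patients measurable outside the marrow only by sFLC, make the more than 90% dFLC reduction a substitute for the M-protein alternatives, using the PR row's construction ("is required in place of the M protein criteria").
- State that patients measurable only in the marrow cannot be scored VGPR from immunofixation and electrophoresis alone.

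Under this rule both hypothetical patients become SD and add nothing to the RR. The second alternative needs no change, and phase I needs no re-scoring. The cost is a short text amendment. All the panels are already collected, so no tests are added. The only downside is a possibly lower reported response rate.

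### Section 8.1 has no partial-response rule for patients whose only measurable M-protein is urinary, so read literally it can score a clear urinary response as stable disease

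*Combined protocol and SAP*

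**What the plan says.** Section 6.1.2, inclusion criterion 4, makes the forms of measurable disease alternatives ("Must have measurable disease defined as any of the following: Serum m-spike" and so on). One of them, sufficient alone, is "24 h urine m-spike of at least 200mg/d".

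Section 8.1 defines PR as at least a 50% "reduction of serum M protein and reduction in 24-h urinary M protein by" at least 90% or to below 200 mg/24 h, so the serum and urine requirements are joined by *and*. There are two substitutes. The free-light-chain criterion applies "if the serum and urine M protein are unmeasurable". The marrow criterion applies "if the only measurable disease is in the bone marrow, a".

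MR joins a 25–49% serum fall to a 50–89% urine fall "which still exceeds 200mg per 24 h". VGPR has three limbs: disappearance on electrophoresis with immunofixation still positive; a serum fall of at least 90% plus urine below 100 mg/24 h; or a light-chain limb for patients with no other measurable disease outside the marrow. Anything short of these that is not progression is stable disease.

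Every response category needs two consecutive blood and urine assessments. For PR or better the second may come at any time, though normally at the next cycle. Section 13.1.2.1 counts sCR, CR, VGPR and PR in the response rate and says reports will mainly list numbers of responses.

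**The concern.** The PR definition is adapted to what was measurable, but one kind of patient admitted by criterion 4 is left out. The gap runs one way. A patient with serum disease and urine already below 200 mg/24 h meets the PR urine clause without difficulty; nothing equivalent helps a patient with urine disease and no serum M-protein.

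Two assessors could therefore grade the same urine-only patient differently, one as stable disease on the literal text and one as PR after waiving the serum clause. Section 8.1 does not decide between them. Section 2 gives a more reliable estimate of activity as one of the aims of the 20-patient extension, and in 20 patients one misgrade is visible in the rate.

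**Working it through.** The plan gives no sample-size or error-rate figure for response, so there is none to reproduce. The check has three parts.

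**1. Literal grading of one case.** Take no serum M-protein and urine falling from 3000 to 50 mg/24 h, confirmed, still visible on electrophoresis. The fall is 1 − 50/3000 = 98.3%.

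- CR: fails, as immunofixation is positive.
- VGPR: the first limb fails (visible on electrophoresis), the second needs a 90% serum fall that is undefined here, and the third needs light chains as the only measurable disease outside the marrow.
- PR: the serum clause is undefined, and neither substitute opens because urine is measurable.
- MR: the serum clause is undefined, and the urine fall is outside 50–89%.
- Result: stable disease.

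Effect on the response rate per patient: 1/20 = 5.0 points in phase II, 1/31 = 3.2 points overall.

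**2. What happens if the serum clause is simply waived.** The PR urine limb of below 200 mg/24 h is the complement of the entry cut-off. The fall needed from baseline b is 1 − 200/b:

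| Baseline (mg/24 h) | 210 | 220 | 250 | 300 | 400 | 1000 | 2000 |
|---|---|---|---|---|---|---|---|
| Fall must exceed | 4.8% | 9.1% | 20% | 33% | 50% | 80% | 90% |

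A PR with a urine fall below 50% is therefore possible only from a baseline below 400 mg/24 h.

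**3. How often noise alone would give a confirmed PR under the waiver.** The within-patient coefficient of variation (CV) of 24-hour urine M-protein is not in the documents and is assumed. Noise is log-normal and independent between visits, with no true change. The observed baseline must be at least 200, and two consecutive values must meet the limb.

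By true level, with 6 panels and two consecutive values below 200:

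| True level (mg/24 h) | CV 20% | CV 30% |
|---|---|---|
| 220 | 42% | 56% |
| 250 | 10% | 28% |
| 300 | 0.3% | 5% |
| 400 | 0.0% | 0.1% |

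Across all urine-only patients, I assumed true levels log-normal with log-SD 1.2, CV 15–35% and 3 or 6 panels, and repeated the simulation with 1,000,000 patients per cell before applying the entry rule:

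| Assumed median (mg/24 h) | Scored PR with no true change |
|---|---|
| 400 | 2.2–8.3% |
| 600 | 1.5–5.7% |
| 1500 | 0.5–1.9% |

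Between 73% and 99% of these came from observed baselines below 300 mg/24 h. If 1 to 4 of 20 patients were urine-only (an assumption), the expected number of such PRs is 1 × 0.005 = 0.005 to 4 × 0.08 = 0.32, or 0.03 to 1.6 points on the rate.

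**The case against.** **The named standard may settle it.** The protocol assesses response by the international uniform criteria, which may say how urine-only disease is graded. That cannot be checked from these documents. If they do, the sponsor-investigator can close the point by writing the rule into 8.1, which is what the protocol directs assessors to and which is silent now.

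**The gap is narrower than all urine-only patients.** This stands. A serum spike below 1 g/dL is not measurable under criterion 4 but can still fall by 50%. CR, and VGPR by disappearance on electrophoresis, need no percentage serum fall. The literal failure concerns patients with no quantifiable serum M-protein whose urine M-protein remains visible.

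**A reader might infer that measurement noise will manufacture responders**, since the PR limb equals the entry cut-off. The documents do not support that as a general statement. The two-consecutive-assessment rule applies, the effect is confined to baselines near 200 mg/24 h, and it is close to nil from about 400. The constant-level model is also generous: progression removes patients, and only one of 11 phase I patients is reported with stable disease for six months.

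**A reader might also want a 50% minimum fall added to the urine limb.** That would depart from the criteria the protocol names. Applied to each measurable component, it would also downgrade patients with both serum and urine disease. With serum falling from 3.0 to 0.6 g/dL (80%) and urine from 300 to 170 mg/24 h (43%), the patient is a PR now and would become stable disease, because MR needs a 25–49% serum fall and urine above 200.

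**A fall from 2000 to 400 mg/24 h (80%) missing PR** is not a fault; it is the 90% threshold doing its job.

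**Conclusion.** The gap is real on the text. Section 6.1.2 admits urine-only disease and section 8.1 supplies no PR, MR or percentage-VGPR route for it when there is no serum M-protein. Each responder lost this way costs 5.0 points of 20 or 3.2 of 31. The number of such patients is not given, so the total effect on the response rate cannot be fixed.

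The overlap of the PR urine limb with the entry cut-off is a smaller, secondary matter: roughly 0.5–8% of urine-only patients under the assumed CVs and medians, mainly with baselines below about 300 mg/24 h. It calls for transparent reporting, not a changed threshold.

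Response is a secondary endpoint, described without a decision rule. This is a minor-to-moderate correction to classification and does not touch the primary safety analysis.

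**What to change.** State in section 8.1 that:

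- the serum and urine clauses of PR, and the matching clauses of MR and VGPR, apply only to components measurable at screening (serum at least 1 g/dL, urine at least 200 mg/24 h);
- a component not measurable at screening need not fall but must not meet progression;
- the PR urine limb (at least 90%, or to below 200 mg/24 h) is unchanged.

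Under this rule the fall from 3000 to 50 mg/24 h is a VGPR, because urine is below 100 mg/24 h, and the fall from 2000 to 400 is an MR. It also opens MR to serum-only patients, who start below 200 mg/24 h in urine and so cannot literally meet the present MR urine clause.

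In the report, list separately any PR in a urine-only patient whose urine fell by less than 50% from screening, and give the number of urine-only patients.

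The cost is a short addition to 8.1 and a re-score of panels already collected. Adopt the rule before phase II responses are tabulated and apply it to every patient, including those already graded. No new assessments are needed.

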Phase II extension: Patients in phase I (median age 65, range 50-73, median previous regimens 5, range 2-10) tolerated treatment without DLT and without non-hematologic severe (grade 3 or higher) adverse event according to CTCAE vs.4.03. Three patients developed grade 3 hematologic toxicities (2 neutropenia, 1 thrombocytopenia). Worst diarrhea was grade 1 (n=6), worst nausea grade 2 (n=1) and 4 additional patients developed transient grade 1 nausea. Other possibly panobinostat or ixazomib related grade 1/2 adverse events included thrombocytopenia (n=5), neutropenia (n=3), fatigue (n=2), anemia (n=2), anorexia (n=1) and arthralgia (n=1).

Median QTcF before treatment start was 405 msec (range 378-430) and increased on average by 4.3% (maximally by 13%). One patient developed transient grade 1 QTcF prolongation to 552 msec. No other cardiac adverse events were observed. Of the 11 patients in phase I, one reached PR, two reached MR, and one had stable disease for 6 months. All patients entered the study with disease refractory to their last regimen, and in two of the responding patients (1PR, 1MR) this included a proteasome inhibitor an IMiD, and a glucocorticosteroid (carfilzomib, pomalidomide, dexamethasone in the MR patient, bortezomib, dexamethasone, lenalidomide in the MR patient). Overall, we are encouraged by activity in extensively pretreated patients and by excellent tolerance of this regimen so far. In phase II we aim to extend the study cohort by an additional 20 patients who will be treated until progression or other reasons for discontinuation arise (7.6.1) to strengthen the safety analysis and obtain a more reliable estimate of activity.

3 Study objectives

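### The minor-response rule in Section 8.1 needs a baseline urine M-protein above 400 mg/24 h and scores some better responses as stable disease, so the clinical benefit response rate can be understated

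*Combined protocol and SAP*

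**What the plan says.** The response table in Section 8.1 of the combined protocol and SAP defines MR as a 25 to 49% "reduction of serum M protein and reduction in 24 h urine M protein by 50–89%, which still exceeds 200mg per 24 h". The closing condition, "which still exceeds 200mg per 24 h", sets a floor under the urine level reached. The serum and urine conditions are joined by 'and'. Only the soft-tissue condition depends on what was there at entry: "if present at baseline, 25–49% reduction in the size of soft tissue plasmacytomas is also required". Stable disease (SD) takes every patient who meets no other category.

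The PR row above it is built differently. It asks for a serum fall of at least 50% and a urine fall of at least 90% or a urine level below 200 mg/24 h. When neither M-protein is measurable, a 50% "decrease in the difference between involved and uninvolved sFLC levels is required in place of the M protein criteria". It has a further route "if the only measurable disease is in the bone marrow". MR has neither substitute.

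Inclusion criterion 4 in Section 6.1.2 reads "Must have measurable disease defined as any of the following" and lists four types: serum M-spike of at least 1 g/dL, urine M-spike of at least 200 mg per day, involved free light chains of at least 100 mg/L with an abnormal ratio, and at least 30% marrow plasma cells.

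Section 13.1.2.1 counts MR in the clinical benefit response rate (CBRR). Section 2 supports the phase II extension partly with MRs: "Of the 11 patients in phase I, one reached PR, two reached MR".

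**The concern.** A response scale should be open to every type of disease that the trial admits, and a patient who does better on every marker should not score lower. The MR rule fails both requirements. Some eligible patients cannot reach MR whatever their course, and others lose MR because a marker improved too much. Both kinds fall into SD.

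CBRR is a named secondary endpoint, and the phase II cohort is meant to give a firmer estimate of activity. If the rule is applied literally, CBRR depends partly on which marker a patient happens to have. If assessors depart from the rule case by case, the reported rate follows a definition that is not written down.

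**Working it through.** The plan gives no figure on this point to reproduce. The check takes the thresholds in the Section 8.1 table and inclusion criterion 4 as inputs and applies the rules literally.

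**Baseline urine M-protein needed for MR.** Let B be the baseline in mg/24 h and r the fractional fall. MR needs B(1 − r) > 200 with 0.50 ≤ r ≤ 0.89, so B > 200/(1 − r):

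- r = 0.50: B > 400
- r = 0.60: B > 500
- r = 0.70: B > 667
- r = 0.80: B > 1000
- r = 0.89: B > 1818

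The least demanding case is 400 mg/24 h, against an entry threshold of 200 mg per day.

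**Which patients can reach MR.**

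- Serum M-protein only: a 40% fall scores SD because the urine condition cannot be met. A 50% fall scores PR, because a urine level below 200 mg satisfies PR. No MR step lies between.
- Urine M-protein only, 1000 to 400 mg: SD, because there is no serum fall to count.
- Light-chain-only or marrow-only disease: no MR rule exists.
- Both proteins measurable, urine 300 to 135 mg (a 55% fall), serum down 40%: SD, because the residual is below 200 mg.

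**Ordering.** The cases below assume no plasmacytoma, no progression and confirmed values. None meets VGPR, which by percentage needs a 90% serum fall with urine below 100 mg.

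| Serum fall | Urine, mg/24 h (fall) | PR met? | MR met? | Score |
|---|---|---|---|---|
| 40% | 1000 to 400 (60%) | No: serum below 50% | Yes | MR |
| 60% | 1000 to 300 (70%) | No: urine fall below 90% and level not below 200 | No: serum above 49% | SD |
| 95% | 1500 to 300 (80%) | No: same reason | No: serum above 49% | SD |
| 40% | 1000 to 150 (85%) | No: serum below 50% | No: residual not above 200 | SD |
| 40% | 3000 to 150 (95%) | No: serum below 50% | No: urine fall above 89%, residual not above 200 | SD |

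Rows 2 to 5 are at least as good as row 1 on both percentage falls and better on one or both, yet they rank below it. The plasmacytoma limit works the same way: a 60% shrinkage fails a condition that a 40% shrinkage meets.

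**Grid check.** Serum falls of 25 to 100% were crossed with urine falls of 50 to 100% in 1-point steps (76 × 51 = 3876 combinations). The number scoring MR was 0 at baseline urine of 0, 200 and 400 mg, 25 × 10 = 250 at 500 mg, 25 × 30 = 750 at 1000 mg, and 25 × 40 = 1000 at 2000 mg. These counts show where MR is possible. They are not patient frequencies.

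**Direction.** Every patient who meets the literal rule also meets the rule proposed under the fix: the serum fall is below 50%, so PR is not met, and each minimum fall is reached. The reverse does not hold. The literal rule can therefore only lower the count of MRs.

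**The case against.** The strongest objection is that the table is shorthand, with each condition meant for whichever marker is measurable. The PR row has the same 'and', and its light-chain substitute applies only when both proteins are unmeasurable. Read with equal strictness, a urine-only patient could not reach PR either, yet such patients are eligible. The protocol also calls the clinical benefit criteria adapted or modified EBMT criteria, and those may settle the matter. This has weight for single-marker patients, where the text may be ambiguous rather than deliberately exclusive. It does not rescue the ordering: in the tabulated cases both proteins are measurable, so shorthand changes nothing. Nor does it help a patient with measurable serum and 200 to 400 mg of urine protein. The outside criteria are not reproduced, and Section 8.1 is the definition to which the objectives point.

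The 200 mg could be read as the size of the fall. The bound would then be 200/0.89 = about 225 mg, but the parallel PR condition concerns the level reached, and the upper limits would still misorder responses.

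A reader might infer from phase I that CBRR drops from 3/11 (27%) to 1/11 (9%). The documents do not support that. They give no marker values for the two MR patients and do not suggest that either failed the rule. Those fractions also add PR to a CBRR formula that, as printed, omits it. A reader might also infer that most patients are shut out of MR, but no mix of disease types is given. Nor is it strictly true that urine-predominant disease can never reach MR: a patient with more than 400 mg of urine protein and a small serum spike below the measurable threshold could qualify.

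Finally, the endpoint is secondary and descriptive, and no test or stopping rule uses it. That limits the consequence but does not remove the defect.

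**Conclusion.** The point holds for the rule as written. MR requires falls in both proteins and a baseline urine M-protein above 400 mg/24 h, a bound that follows exactly from the stated limits. The rule offers no route for light-chain-only or marrow-only disease, and it ranks some better responses below worse ones. The misordering does not depend on how single-marker patients are read.

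The effect on CBRR is downward only. Its size cannot be computed, because that would need the distribution of marker types and patient-level values, and the documents give neither. The primary endpoint of dose-limiting toxicity and tolerance is untouched. The change should be made, but it is not critical to the trial's main conclusion.

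Separately, the CBRR formula in Section 13.1.2.1 lists sCR, CR, VGPR and MR but not PR, although Section 1.1 describes clinical benefit as at least a minor response. CBRR is not meaningful until that is corrected too.

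**What to change.** In Section 8.1, define MR as all of the following:

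- PR or better not met
- at least a 25% fall in serum M-protein, if measurable at baseline
- at least a 50% fall in 24-hour urine M-protein, if measurable at baseline
- at least a 25% reduction of any plasmacytoma present at baseline

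Take measurable from inclusion criterion 4. Remove the upper limits and the condition that urine stay above 200 mg. Keep the existing 6-week confirmation and the lytic-lesion condition.

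State that patients with only light-chain or only marrow disease are not assessable for MR. Without that statement they would meet the two conditional M-protein items by default. Report CBRR with and without these patients in the denominator. This is preferable to a new light-chain or marrow threshold, which the documents do not contain. For marrow-only disease a threshold would also clash with the 6-week confirmation, because marrow is scheduled only after cycle 2 and at study end.

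Add PR to the CBRR formula in Section 13.1.2.1 in the same amendment, and rescore phase I under the revised rule so that the whole-study rate uses one definition.

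The cost is a short text change and re-derivation of MR from stored results. Serum and urine electrophoresis and free light chains are already scheduled each cycle in Table 8-1, so no new tests are needed and patient management does not change.
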